10.7. Appendix 7: ECG Findings of Potential Clinical Concern

ECG Findings That May Qualify as AEs

 Marked sinus bradycardia (rate <40 bpm) lasting minutes. New PR interval prolongation >280 msec. New prolongation of QTcF to >480 msec (absolute) or by \geq60 msec from baseline. New-onset atrial flutter or fibrillation, with controlled ventricular response rate: ie, rate <120 bpm. New-onset type I second-degree (Wenckebach) AV block of >30 seconds' duration. Frequent PVCs, triplets, or short intervals (<30 seconds) of consecutive ventricular complexes.
ECG Findings That May Qualify as SAEs

 QTcF prolongation >500 msec. New ST-T changes suggestive of myocardial ischemia. New-onset left bundle branch block (QRS >120 msec). New-onset right bundle branch block (QRS >120 msec). Symptomatic bradycardia. Asystole: 
 In awake, symptom-free participants in sinus rhythm, with documented periods of asystole \geq3.0 seconds or any escape rate <40 bpm, or with an escape rhythm that is below the AV node. In awake, symptom-free participants with atrial fibrillation and bradycardia with 1 or more pauses of at least 5 seconds or longer. Atrial flutter or fibrillation, with rapid ventricular response rate: rapid = rate >120 bpm. Sustained supraventricular tachycardia (rate >120 bpm) ("sustained" = short duration with relevant symptoms or lasting >1 minute).

- Ventricular rhythms >30 seconds' duration, including idioventricular rhythm (heart rate <40 bpm), accelerated idioventricular rhythm (HR >40 bpm to <100 bpm), and monomorphic/polymorphic ventricular tachycardia (HR >100 bpm (such as torsades de pointes)).
- Type II second-degree (Mobitz II) AV block.
- Complete (third-degree) heart block.

ECG Findings That Qualify as SAEs

- Change in pattern suggestive of new myocardial infarction.
- Sustained ventricular tachyarrhythmias (>30 seconds' duration).
- Second- or third-degree AV block requiring pacemaker placement.
- Asystolic pauses requiring pacemaker placement.
- Atrial flutter or fibrillation with rapid ventricular response requiring cardioversion.
- Ventricular fibrillation/flutter.
- At the discretion of the investigator, any arrhythmia classified as an adverse experience.

The enumerated list of major events of potential clinical concern are recommended as “alerts” or notifications from the core ECG laboratory to the investigator and Pfizer study team, and not to be considered as all inclusive of what to be reported as AEs/SAEs.

10.8. Appendix 8: Abbreviations

The following is a list of abbreviations that may be used in the protocol.

Abbreviation	Term
Abs	absolute
ADA	antidrug antibodies
ADL	activities of daily living
AE	adverse event
ALT	alanine aminotransferase
aPTT	activated partial thromboplastin time
AST	aspartate aminotransferase
AUC	area under the concentration-time curve
AUC _{14day}	AUC from time 0 to 14 days post-dose
AUC _{28day}	AUC from time 0 to 28 days post-dose
AUC _{inf}	AUC from time 0 extrapolated to infinite time
AUC _{last}	AUC from time 0 to the time of the last quantifiable concentration
AUC _τ	AUC from time 0 to time τ , the dosing interval
AV	atrioventricular
β-hCG	beta-human chorionic gonadotropin
BMI	body mass index
BP	blood pressure
bpm	beats per minute
BUN	blood urea nitrogen
C _{av}	concentration average
CFR	Code of Federal Regulations
CIOMS	Council for International Organizations of Medical Sciences
CK	creatine kinase
CL	clearance
C _{max}	maximum observed concentration
CMV	cytomegalovirus
COVID-19	coronavirus disease 2019
CRF	case report form
CRO	contract research organization
CRU	clinical research unit
CSR	Clinical Study Report
CT	computed tomography
CT SAE	clinical trial serious adverse event (report form)
DILI	drug-induced liver injury
DM	dermatomyositis
DMC	Data Monitoring Committee
dn	dose normalized
DNA	deoxyribonucleic acid

Abbreviation	Term
EBV	Epstein-Barr virus
EC	Ethics Committee
ECC	emergency contact card
ECG	electrocardiogram
eCRF	electronic case report form
EDB	exposure during breastfeeding
EDP	exposure during pregnancy
EMA	European Medicines Agency
ePPND	enhanced pre and postnatal development
ET	early termination
EU	European Union
EudraCT	European Union Drug Regulating Authorities Clinical Trials (European Clinical Trials Database)
FSH	follicle-stimulating hormone
GCP	Good Clinical Practice
GGT	gamma-glutamyl transferase
GLP	Good Laboratory Practice
HBcAb	hepatitis B core antibody
HBsAb	hepatitis B surface antibody
HBsAg	hepatitis B surface antigen
HBV	hepatitis B virus
HBV DNA	hepatitis B virus DNA
HCVAb	hepatitis C antibody
HHV6	human herpesvirus 6
HIV	human immunodeficiency virus
HR	heart rate
HRT	hormone replacement therapy
HSV-1	herpes simplex virus type 1
HSV-2	herpes simplex virus type 2
IB	Investigator's Brochure
ICD	informed consent document
ICH	International Council for Harmonisation
ID	identification
IFN	interferon
IFNAR	Type 1 interferon α/β receptor
IgG	immunoglobulin G
IGRA	Interferon-Gamma Release Assays
IMP	investigational medicinal product
IND	Investigational New Drug
INR	international normalized ratio
IP manual	investigational product manual

Abbreviation	Term
IPAL	Investigational Product Accountability Log
IRB	Institutional Review Board
IRR	infusion related reaction
IV	intravenous(ly)
JAK	Janus kinase
k_{el}	terminal phase rate constant
LBBB	left bundle branch block
LFT	liver function test
MAD	multiple ascending dose
MCH	mean corpuscular hemoglobin
MCHC	mean corpuscular hemoglobin concentration
MCV	mean corpuscular volume
MRI	magnetic resonance imaging
MRT	mean residence time
msec	millisecond
N/A	not applicable
NAb	neutralizing antibodies
NIMP	noninvestigational medicinal product
PCR	polymerase chain reaction
PD	pharmacodynamic(s)
PK	pharmacokinetic(s)
PR	pulse rate
PT	prothrombin time
PVC	premature ventricular contraction/complex
Q2W	once every 2 weeks
Q4W	once every 4 weeks
QFT-G	QuantiFERON®-TB Gold In Tube
QTc	corrected QT
QTcF	corrected QT (Fridericia method)
qual	qualitative
R_{ac}	accumulation ratio for AUC_{τ}
R_{ac}, C_{max}	accumulation ratio for C_{max}
RBC	red blood cell
CCI	[REDACTED]
SAD	single ascending dose
SAE	serious adverse event
SAP	Statistical Analysis Plan
SARS-CoV-2	severe acute respiratory syndrome coronavirus 2
SC	subcutaneous(ly)
SLE	systemic lupus erythematosus
SoA	schedule of activities

Abbreviation	Term
SOP	standard operating procedure
SRSD	single reference safety document
SUSAR	suspected unexpected serious adverse reaction
TB	tuberculosis
TBili	total bilirubin
TEAE	treatment emergent adverse event
$t_{1/2}$	terminal phase half-life
THC	tetrahydrocannabinol
T_{max}	time to reach C_{max}
T-Spot	T-spot [®] TB
ULN	upper limit of normal
US	United States
V_{ss}	volume at steady state
VZV	varicella-zoster virus
WBC	white blood cell
WOCBP	woman of childbearing potential

1. VERSION HISTORY

Table 1. Summary of Changes

Version/ Date	Associated Protocol Amendment	Rationale	Specific Changes
1 21JUL2021	Original 26MAY2021 Amendment 1 09JUL2021	N/A	N/A
2 14APR2022	N/A	Some clarifications were added.	Section 6.1.1: Added clarification on the definition of IRR and viral infections. Sections 6.1.3 and 6.1.4: The categorical classes for vital signs and ECGs were specified in Appendix 1. Overall: Minor edits for the description maintenance.

2. INTRODUCTION

This statistical analysis plan (SAP) provides the detailed methodology for summary and statistical analyses of the data collected in Study C0251005. This document may modify the plans outlined in the protocol; however, any major modifications of the primary endpoint definition or its analysis will also be reflected in a protocol amendment.

2.1. Study Objectives, Endpoints, and Estimands

The following are objectives and endpoints in this study. Estimand framework is not applied to this phase 1 study.

Objectives	Endpoints
Primary:	Primary:

 To evaluate the safety and tolerability of single IV dose of 300 and 900 mg PF-06823859 in Japanese healthy participants. 	
 Assessments of AEs/SAEs including IRR, infusion sites and viral infections, vital signs, ECGs and laboratory tests.
Secondary:	Secondary:

 To evaluate the PK profile of single IV dose of 300 and 900 mg PF-06823859 in Japanese healthy participants. To evaluate the immunogenicity of PF-06823859. 	
 Serum PF-06823859 PK parameters, as permitted by data: C_{max}, C_{max} (dn), T_{max}, AUC_{inf}, AUC_{inf} (dn), AUC_{last}, AUC_{last} (dn), AUC_{14day}, AUC_{28day}, $t_{1/2}$, CL, V_{ss} and MRT Incidence of the development of ADA and NAb.

PFIZER GENERAL BUSINESS

(dn: dose normalized)

2.2. Study Design

This is a Phase 1, randomized, double-blind, sponsor-open, placebo-controlled study to evaluate the safety, tolerability, immunogenicity and PK of PF-06823859 in Japanese healthy adult participants.

[figure not shown]
Approximately 12 participants are planned to be enrolled into the study. The study consists of 2 cohorts, and approximately 5 participants will be randomized to PF-06823859 and approximately 1 participant will be randomized to placebo in each cohort. Participants who discontinue prior to completion of the study for non-safety related reasons may be replaced at the discretion of the investigator upon consultation with the sponsor. Each participant will receive PF-06823859 or placebo per the scheme summarized in Table 2.

Table 2. Randomization Scheme

Cohort	Treatment	Number of participants
1	PF-06823859 300 mg	5
	Placebo	1
2	PF-06823859 900 mg	5
	Placebo	1

Within 28 days of successful completion of the screening process, eligible participants will be enrolled and randomized to receive a single IV infusion of PF-06823859 or placebo. The participants in Cohort 2 should be dosed following at least 96 hours safety pause after the participants in Cohort 1 have been dosed. Participants will be admitted into the clinical research unit (CRU) approximately 1 day prior to dosing and are required to stay overnight in the CRU through completion of Day 5 evaluations. Participants will return to the CRU for outpatient follow up visits per Schedule of Activities given in the protocol through Day 157. Participants may be asked to return for additional follow up visits beyond the anticipated end of study visit for safety reasons and/or at the discretion of the investigator.

PFIZER GENERAL BUSINESS

3. ENDPOINTS AND BASELINE VARIABLES: DEFINITIONS AND CONVENTIONS

3.1. Primary Endpoint(s)

Primary endpoints are assessments of AEs/SAEs including IRR, infusion sites and viral infections, vital signs, ECGs and laboratory tests.

3.2. Secondary Endpoint(s)

Secondary endpoints are:

- Serum PF-06823859 PK parameters, as permitted by data: C_{max} , C_{max} (dn), T_{max} , AUC_{inf} , AUC_{inf} (dn), AUC_{last} , AUC_{last} (dn), AUC_{14day} , AUC_{28day} , $t_{1/2}$, CL , V_{ss} and MRT. Definition and method of determination of PK parameters are shown in Table 3. PK parameters which will be calculated as permitted by data are also specified in Table 3.
- Incidence of the development of ADA and NAb.

Table 3. Serum PF-06823859 PK Parameters

Parameter	Definition	Method of Determination
AUC_{14day}	Area under the serum concentration-time profile from time 0 to 14 days post-dose (336 hours)	Linear/Log trapezoidal method
AUC_{28day}	Area under the serum concentration-time profile from time 0 to 28 days post-dose (672 hours)	Linear/Log trapezoidal method
AUC_{last}	Area under the serum concentration-time profile from time 0 to the time of the last quantifiable concentration (C_{last})	Linear/Log trapezoidal method
AUC_{last} (dn)	Dose normalized AUC_{last}	$AUC_{last}/Dose$
AUC_{inf}^a	Area under the serum concentration-time profile from time 0 extrapolated to infinite time	$AUC_{last} + (C_{last}^* / k_{el})$, where C_{last}^* is the predicted serum concentration at the last quantifiable time point estimated from the log-linear regression analysis
AUC_{inf} (dn)	Dose normalized AUC_{inf}	$AUC_{inf}/Dose$
C_{max}	Maximum serum concentration	Observed directly from data
C_{max} (dn)	Dose normalized C_{max}	$C_{max}/Dose$

PFIZER GENERAL BUSINESS

Table 3. Serum PF-06823859 PK Parameters

Parameter	Definition	Method of Determination
T _{max}	Time at which C _{max} occurs	Observed directly from data as time of first occurrence
t _{1/2} ^a	Terminal half-life	Log _e (2)/k _{el} , where k _{el} is the terminal phase rate constant calculated by a linear regression of the log-linear concentration-time curve
CL ^a	Clearance	Dose/AUC _{inf}
V _{ss} ^a	Volume of distribution at steady state	CL*MRT
MRT	Mean residence time	AUMC _{inf} /AUC _{inf} – DOF/2, where AUMC _{inf} is the area under the moment curve from time 0 extrapolated to infinity and DOF is the duration of the IV infusion.

a. If data permitted.

3.3. Other Endpoint(s)

N/A

3.4. Baseline Variables

There are no baseline variables used as covariates or stratification factors in this study.

The demographic data will include age, sex, ethnicity, race, weight, body mass index and height. If not specified, baseline variables are those collected on Day 1 prior to dosing or last measurement during screening visits and Day -1.

3.5. Safety Endpoints

[figure not shown]
3.5.1. Adverse Events

An adverse event is considered a treatment-emergent adverse event (TEAE) to a given treatment if the event starts on or after the first dosing day and time/start time, if collected, but before the last dose plus the lag time. The algorithm will not consider any events that started prior to the first dose date. If an AE starts on the same day as the first dose date, it will be considered treatment emergent unless the CRF data indicates otherwise via explicitly recording time for AE onset and treatment dosing. The default lag time of CDISC and Pfizer Standards (CaPS) will be used for this study.

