5.2. Exclusion Criteria

Participants are excluded from the study if any of the following criteria apply:

Medical Conditions:

1. Evidence or history of clinically significant hematological, renal, endocrine, pulmonary, gastrointestinal, cardiovascular, hepatic, psychiatric, neurological, or allergic disease (including drug allergies, but excluding untreated, asymptomatic, seasonal allergies at the time of dosing).
2. History of HIV infection, hepatitis C or syphilis; positive testing for HIV, HCVAb or syphilis at screening.
3. Infection with HBV as defined in [Section 8.2.6.1](#).
4. Clinically significant abnormality, including but not limited to current, active TB or previous inactive TB, general infections, heart failure or malignancy, on chest X-ray performed at screening or within 12 weeks of screening.
5. History of autoimmune disorders.
6. History of allergic or anaphylactic reaction to a therapeutic drug or any components in the study intervention.
7. Participants with clinically significant infections, based on which the investigator judges that the participant should not be enrolled in the study, within 28 days prior to the screening visit.
8. Participants with a fever, based on which the investigator judges that the participant should not be enrolled in the study, within the last 7 days prior to dosing.
9. Participants who have evidence of TB infection as defined in [Section 8.2.7](#).
 - Participants who have been treated or are currently being treated for active or latent TB infection are to be excluded.
 - Participants with a history of either untreated or inadequately treated latent or active TB infection are to be excluded.

10. Other medical or psychiatric condition including recent (within the past year) or active suicidal ideation/behavior or laboratory abnormality or other conditions or situations related to COVID-19 pandemic (eg, Contact with positive case, residence, or travel to an area with high incidence) that may increase the risk of study participation or, in the investigator's judgment, make the participant inappropriate for the study.

Prior/Concomitant Therapy:

11. Use of prescription or nonprescription drugs and dietary and herbal supplements within 7 days or 5 half-lives (whichever is longer) prior to the first dose of study intervention. (Refer to [Section 6.8](#) for additional details).
12. Recent exposure to any live or attenuated live virus vaccines within 6 weeks of admission to CRU.

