8. STUDY ASSESSMENTS AND PROCEDURES

The investigator (or an appropriate delegate at the investigator site) must obtain a signed and dated ICD before performing any study-specific procedures.

Study procedures and their timing are summarized in the [SoA](#). Protocol waivers or exemptions are not allowed.

Safety issues should be discussed with the sponsor immediately upon occurrence or awareness to determine whether the participant should continue or discontinue study intervention.

Adherence to the study design requirements, including those specified in the [SoA](#), is essential and required for study conduct.

All screening evaluations must be completed and reviewed to confirm that potential participants meet all eligibility criteria. The investigator will maintain a screening log to record details of all participants screened and to confirm eligibility or record reasons for screening failure, as applicable.

Participants will be screened within 28 days prior to administration of the study intervention to confirm that they meet the study population criteria for the study. If the time between screening and dosing exceeds 28 days as a result of unexpected delays (eg, delayed drug shipment), then participants do not require rescreening if the laboratory results obtained prior to first dose administration meet eligibility criteria.

A participant who qualified for this protocol but did not enroll from an earlier cohort/group may be used in a subsequent cohort/group without rescreening, provided laboratory results obtained prior to the first dose administration meet eligibility criteria for this study. In addition, other clinical assessments or specimen collections, eg, banked biospecimens, may be used without repeat collection, as appropriate.

Every effort should be made to ensure that protocol-required tests and procedures are completed as described. However, it is anticipated that from time to time there may be circumstances outside the control of the investigator that may make it unfeasible to perform the test. In these cases, the investigator must take all steps necessary to ensure the safety and well-being of the participant. When a protocol-required test cannot be performed, the investigator will document the reason for the missed test and any corrective and preventive actions that he or she has taken to ensure that required processes are adhered to as soon as possible. The study team must be informed of these incidents in a timely manner.

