8.3.1. Time Period and Frequency for Collecting AE and SAE Information

The time period for actively eliciting and collecting AEs and SAEs (“active collection period”) for each participant begins from the time the participant provides informed consent, which is obtained before the participant’s participation in the study (ie, before undergoing any study-related procedure and/or receiving study intervention), through and including a minimum of 150 calendar days, except as indicated below, after the last administration of the study intervention.

Follow-up by the investigator continues throughout and after the active collection period and until the AE or SAE or its sequelae resolve or stabilize at a level acceptable to the investigator.

For participants who are screen failures, the active collection period ends when screen failure status is determined.

If the participant withdraws from the study and also withdraws consent for the collection of future information, the active collection period ends when consent is withdrawn.

If a participant permanently discontinues or temporarily discontinues study because of an AE or SAE, the AE or SAE must be recorded on the CRF and the SAE reported using the CT SAE Report Form.

Investigators are not obligated to actively seek information on AEs or SAEs after the participant has concluded study participation. However, if the investigator learns of any SAE, including a death, at any time after a participant has completed the study, and he/she

considers the event to be reasonably related to the study intervention, the investigator must promptly report the SAE to Pfizer using the CT SAE Report Form.

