10.3.1. Definition of AE

AE Definition

• An AE is any untoward medical occurrence in a patient or clinical study participant, temporally associated with the use of study intervention, whether or not considered related to the study intervention.• Note: An AE can therefore be any unfavorable and unintended sign (including an abnormal laboratory finding), symptom, or disease (new or exacerbated) temporally associated with the use of study intervention.

Events Meeting the AE Definition

• Any abnormal laboratory test results (hematology, clinical chemistry, or urinalysis) or other safety assessments (eg, ECG, radiological scans, vital sign measurements), including those that worsen from baseline, considered clinically significant in the medical and scientific judgment of the investigator. Any abnormal laboratory test results that meet any of the conditions below must be recorded as an AE:
• Is associated with accompanying symptoms;• Requires additional diagnostic testing or medical/surgical intervention;• Leads to a change in study dosing (outside of any protocol-specified dose adjustments) or discontinuation from the study, significant additional concomitant drug treatment, or other therapy.• Exacerbation of a chronic or intermittent preexisting condition, including either an increase in frequency and/or intensity of the condition.• New condition detected or diagnosed after study intervention administration, even though it may have been present before the start of the study.• Signs, symptoms, or the clinical sequelae of a suspected drug-drug interaction.• Signs, symptoms, or the clinical sequelae of a suspected overdose of either study intervention or a concomitant medication. Overdose per se will not be reported as an AE or SAE unless it is an intentional overdose taken with possible suicidal/self-harming intent. Such overdoses should be reported regardless of sequelae.

Events NOT Meeting the AE Definition

- Any clinically significant abnormal laboratory findings or other abnormal safety assessments that are associated with the underlying disease, unless judged by the investigator to be more severe than expected for the participant's condition.
- The disease/disorder being studied or expected progression, signs, or symptoms of the disease/disorder being studied, unless more severe than expected for the participant's condition.

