* **EDP** (with or without an associated AE or SAE): any pregnancy information is reported to Pfizer Safety using CT SAE Report Form and EDP Supplemental Form; if the EDP is associated with an SAE, then the SAE is reported to Pfizer Safety using the CT SAE Report Form.

** **EDB** is reported to Pfizer Safety using the CT SAE Report Form which would also include details of any SAE that might be associated with the EDB.

*** **Environmental or Occupational exposure:** AEs or SAEs associated with occupational exposure are reported to Pfizer Safety using the CT SAE Report Form.

- When an AE or SAE occurs, it is the responsibility of the investigator to review all documentation (eg, hospital progress notes, laboratory reports, and diagnostic reports) related to the event.

- The investigator will then record all relevant AE or SAE information in the CRF.
- It is **not** acceptable for the investigator to send photocopies of the participant's medical records to Pfizer Safety in lieu of completion of the CT SAE Report Form/AE or SAE CRF page.
- There may be instances when copies of medical records for certain cases are requested by Pfizer Safety. In this case, all participant identifiers, with the exception of the participant number, will be redacted on the copies of the medical records before submission to Pfizer Safety.
- The investigator will attempt to establish a diagnosis of the event based on signs, symptoms, and/or other clinical information. Whenever possible, the diagnosis (not the individual signs/symptoms) will be documented as the AE or SAE.

Assessment of Intensity

The investigator will make an assessment of intensity for each AE and SAE reported during the study and assign it to 1 of the following categories:

- Mild: Asymptomatic or mild symptoms; clinical or diagnostic observations only; intervention not indicated.
- Moderate: Minimal, local or noninvasive intervention indicated; limiting age-appropriate instrumental ADL. Instrumental ADL refers to preparing meals, shopping for groceries or clothes, using the telephone, managing money, etc.
- Severe: Severe or medically significant but not immediately life-threatening; hospitalization or prolongation of hospitalization indicated; disabling, limiting self care ADL. Self care ADL refers to bathing, dressing and undressing, feeding self, using the toilet, taking medications, and not bedridden.

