- The investigator is obligated to perform or arrange for the conduct of supplemental measurements and/or evaluations, as medically indicated or as requested by the sponsor, to elucidate the nature and/or causality of the AE or SAE as fully as possible. This may include additional laboratory tests or investigations, histopathological examinations, or consultation with other healthcare providers.
- If a participant dies during participation in the study or during a recognized follow-up period, the investigator will provide Pfizer Safety with a copy of any postmortem findings, including histopathology.

- New or updated information will be recorded in the originally submitted documents.
- The investigator will submit any updated SAE data to the sponsor within 24 hours of receipt of the information.

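### SAP 3.5.1 has no worsening clause, so an acute adverse event ongoing at infusion that then worsens is treatment-emergent only if the site enters the worsening as a new event

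*SAP*

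**What the plan says.** SAP 3.5.1 counts an event as treatment-emergent if it starts at or after first dosing and before the last dose plus a lag time. A Day 1 event counts unless recorded times show that it began before dosing. The section then states: "The algorithm will not consider any events that started prior to the first dose date". Severity plays no part in the rule.

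Protocol 8.3.1 says that active collection "begins from the time the participant provides informed consent", so events with pre-dose onset will be on file. Protocol 8 allows screening up to 28 days before dosing. It also covers longer gaps ("If the time between screening and dosing exceeds 28 days as a result of unexpected delays"), in which case rescreening is not needed if the pre-dose laboratory results still qualify.

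On recording, Protocol 10.3.3 has the investigator make an "assessment of intensity for each AE and SAE reported during the study and assign it to 1 of the following categories". For follow-up it says: "New or updated information will be recorded in the originally submitted documents". Protocol 10.3.1 lists among the events that meet the definition: "Exacerbation of a chronic or intermittent preexisting condition, including either an increase in frequency and/or intensity of the condition". The general note in that section also admits exacerbated as well as new disease, without limiting this to chronic conditions. The list of exclusions there removes expected fluctuations of conditions present at study start only where they do not worsen.

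SAP 3.1 makes adverse events, including viral infections, part of the primary endpoint. SAP 6.1.1 lists and summarizes adverse events according to the sponsor's data standards (CaPS), which are not among the documents.

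**The concern.** A treatment-emergent count is normally meant to show what appeared or got worse after dosing. This rule covers only what appeared. A mild infection present at dosing that becomes moderate after infusion is a post-dose deterioration, yet under its pre-dose onset date it is not treatment-emergent.

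Infection is the event type of interest here. Protocol 2.3 names viral infection as a potential risk of blocking this cytokine. Protocol 2.2.2.1 reports that mild upper respiratory tract infection appeared more frequent on drug in the earlier healthy-participant study. Where the rule applies, the count can only go down.

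The other primary safety domains do look at change from the pre-dose state. SAP 3.5.2 takes the baseline result into account for laboratory tests, and SAP 3.5.3 and 3.5.4 use change from baseline for vital signs and ECGs. Only the adverse event rule has no counterpart.

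**Working it through.** The plan states no TEAE rate, power or test, so there is no figure of its own to reproduce. The check applies the rule to example patterns and then works out the weight of one participant.

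**Inputs.** Dosing is on Day 1. The TEAE rule is from SAP 3.5.1. The arm sizes are from SAP 2.2: 5 on 300 mg, 5 on 900 mg, and 1 + 1 = 2 on placebo, pooled under SAP 5.2. The total is 2 × (5 + 1) = 12. Day 2 is taken to lie inside the lag window.

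**Step 1: apply the rule.**

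| Pattern | Rule as written | With a worsening clause |
|---|---|---|
| Onset Day -3, worsens Day 2, one record | Not TEAE | TEAE |
| Onset Day -3, worsening entered as a new record with onset Day 2 | TEAE | TEAE |
| Onset Day -3, no worsening | Not TEAE | Not TEAE |
| Onset Day 2 | TEAE | TEAE |

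Rows 1 and 2 are the same clinical course. They differ only in how the site entered it, and under the present rule they are classified differently. A worsening clause removes that difference and leaves rows 3 and 4 unchanged.

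**Step 2: does either document require the row 2 entry?** The definition in Protocol 10.3.1 permits it: expressly for chronic or intermittent conditions, and through the general note for others. No passage in either document says that worsening of an acute, already recorded event must get its own record and onset date.

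**Step 3: size of one case.** One participant is 1/5 = 20 percentage points in either active arm and 1/2 = 50 points in pooled placebo. For example, if one other participant in an arm of 5 has a TEAE, the reported incidence is 1/5 = 20% instead of 2/5 = 40%. If the affected participant has another TEAE, participant incidence does not change.

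**The case against.** The strongest reply is that the protocol already handles worsening, that the case will hardly occur, and that no planned table is shown to be affected.

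*The definition covers it.* Exacerbated disease can be an adverse event in its own right, and an investigator who enters it with its post-dose start makes it a TEAE. This stands as far as permission goes. It does not supply a requirement.

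*The recording rules do not lock in the pre-dose date.* A reader might infer from the single intensity category and from the instruction on updates that a worsening must keep its original onset. The documents do not say so. The update sentence appears among follow-up and SAE reporting duties and says where new information is placed. The intensity sentence does not bar a second event.

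*Eligibility catches it.* A reader might infer that infections starting after screening go largely unchecked. Exclusion 7 concerns clinically significant infections for which the investigator judges that "the participant should not be enrolled in the study, within 28 days prior to the screening visit". Exclusion 8 concerns fever for which the participant "should not be enrolled in the study, within the last 7 days prior to dosing". Neither expressly bars a mild afebrile infection that starts later. However, the Schedule of Activities repeats the eligibility check on Day -1, with a physical examination, a history update and a COVID-19 questionnaire that covers symptoms. Inclusion 3 requires general good health, exclusion 10 leaves room for judgment, and a PCR test precedes admission. These checks make the case rare but do not change how it would be classified.

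*No output is named.* SAP section 6 does not call its adverse event tables TEAE tables. Under SAP 6.1.1, infusion related reactions come from blind medical review and viral infections from a targeted event list. A reader might infer that those two tables lose events, but the text does not limit them to TEAEs. Adverse events are also listed. All of this stands and confines the point to the treatment-emergent count.

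*Unseen documents may settle it.* CaPS, or the CRF Completion Requirements mentioned in Protocol 10.1.6, may say how worsening is entered or tabulated. That is possible, but SAP 3.5.1 does not refer to either on this matter.

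**Conclusion.** The point holds in a narrow form. Followed as written, SAP 3.5.1 can leave a post-infusion worsening out of the treatment-emergent count, and whether it does so depends on site data entry. This is a rule that can give a wrong count in a primary safety domain, not merely a missing detail.

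The 20-point and 50-point figures rest on three assumptions: a TEAE incidence is reported, the worsening was not entered as a new event, and the participant has no other TEAE.

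The documents give no frequency, and two tempting figures do not supply one. Pre-dose collection of up to 28 days, against 156 days from Day 1 to Day 157, is 28/(28 + 156) = 15% of planned collection time. That is a share of calendar time, not of events that start before dosing, pass the Day -1 checks, are still ongoing at infusion and then worsen. An assumed risk of 1% to 3% per participant would give a chance of at least one case among 12 of 1 - 0.99^12 = 11% to 1 - 0.97^12 = 31%, but this only restates the assumption.

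A reader might also infer that the unstated CaPS lag cuts off late events. Nothing in the documents shows such truncation, and it is not part of this finding.

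**What to change.** In SAP 3.5.1, replace the quoted sentence with:

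> An AE with onset before the start of infusion is not treatment-emergent unless it increases in severity or becomes serious after the start of infusion; such worsening is entered as a new, linked AE record with its post-dose onset date and new severity, and that record is treatment-emergent if it starts within the TEAE window.

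Put the same entry instruction in the CRF Completion Requirements, so that the rule can be programmed and does not depend on site habit.

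The cost is one sentence in the SAP and one line in the CRF guidance. If adverse event records already exist, one query is needed on events with pre-dose onset still ongoing at dosing, among about 12 participants. The downside is that one episode then has two linked records, so event counts rise by one while participant counts do not gain a duplicate. Stating the CaPS default lag in days would be a useful clarification, but it is optional.
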